### **3.6. Missing Data and Outliers**

#### **3.6.1. Missing Data**

In general, missing data will not be imputed unless methods for handling missing data are specified. Exceptions are presented in this document.

For missing last dosing date of study drug, imputation rules are described in Section 4.2.1. The handling of missing or incomplete dates for AE onset is described in Section 7.1.5.2, and for prior and concomitant medications in Section 7.4. The handling of missing data in analyses of the efficacy endpoints is discussed in Section 6.

#### **3.6.2. Outliers**

Outliers will be identified during the data management and data analysis process, but no sensitivity analyses will be conducted. All data will be included in the data analysis.

### **3.7. Data Handling Conventions and Transformations**

In general, age (in years) on the date of the first dose of study drug will be used for analyses and presentation in listings. If an enrolled subject was not dosed with any study drug, the randomization date will be used instead of the first dosing date of study drug. For screen failures, the date the informed consent was signed will be used for age calculation. If only the birth year is collected on the eCRF, “01 January” will be used for the unknown birth day and month for the purpose of age calculation. If only birth year and month are collected, “01” will be used for the unknown birth day.

Non-PK data that are continuous in nature but are less than the lower limit of quantitation (LOQ) or above the upper LOQ will be imputed as follows:

- A value that is 1 unit less than the LOQ will be used to calculate descriptive statistics if the datum is reported in the form of “< x” (where x is considered the LOQ). For example, if the values are reported as < 50 and < 5.0, values of 49 and 4.9, respectively, will be used to calculate summary statistics. An exception to this rule is any value reported as < 1 or < 0.1, etc. For values reported as < 1 or < 0.1, a value of 0.9 or 0.09, respectively, will be used to calculate summary statistics.
- A value that is 1 unit above the LOQ will be used to calculate descriptive statistics if the datum is reported in the form of “> x” (where x is considered the LOQ). Values with decimal points will follow the same logic as above.
- The LOQ will be used to calculate descriptive statistics if the datum is reported in the form of “≤ x” or “≥ x” (where x is considered the LOQ).

If methods based on the assumption that the data are normally distributed are not adequate, analyses may be performed on transformed data or nonparametric analysis methods may be used, as appropriate.

Plasma concentration values that are below the limit of quantitation (BLQ) will be presented as “BLQ” in the concentration data listing. Values that are BLQ will be treated as 0 at pre-dose time points, and one-half the value of the LOQ at post-baseline time points.

The following conventions will be used for the presentation of summary and order statistics:

- If at least 1 subject has a concentration value of BLQ for the time point, the minimum value will be displayed as “BLQ.”
- If more than 25% of the subjects have a concentration data value of BLQ for a given time point, the minimum and Q1 values will be displayed as “BLQ.”
- If more than 50% of the subjects have a concentration data value of BLQ for a given time point, the minimum, Q1, and median values will be displayed as “BLQ.”
- If more than 75% of the subjects have a concentration data value of BLQ for a given time point, the minimum, Q1, median, and Q3 values will be displayed as “BLQ.”
- If all subjects have concentration data values of BLQ for a given time point, all order statistics (minimum, Q1, median, Q3, and maximum) will be displayed as “BLQ.”

### **3.8. Analysis Visit**

#### **3.8.1. Definition of Study Day**

Study day will be calculated from the first dosing date of study drug and derived as follows:

- For postdose study days: Assessment Date – First Dosing Date + 1
- For days prior to the first dose: Assessment Date – First Dosing Date

Therefore, study day 1 is the day of first dose of study drug administration.

#### **3.8.2. Analysis Visit**

The nominal visit as recorded on the eCRF will be used when data are summarized by visit. Any data relating to unscheduled visits will not be assigned to a particular visit or time point. However, the following exception will be made:

- An unscheduled visit prior to the first dosing of study drug may be included in the calculation of the baseline value, if applicable.
- Unscheduled visits after the first dose of study drug will be included in determining the maximum post-baseline toxicity grade.

- For subjects who prematurely discontinue from the study, early termination (ET) data will be assigned to the next scheduled visit where the respective data were scheduled to be collected.
- Data collected on an extended viral load monitoring visit will be summarized as a separate visit, and labeled as Day 35, 42, 49, and 56.

### **3.8.3. Selection of Data in the Event of Multiple Records**

Depending on the statistical analysis method, single values may be required for each analysis visit. If multiple valid, nonmissing, continuous measurements exist in an analysis window, records will be chosen based on the following rules if a single value is needed:

- In general, the baseline value will be the last nonmissing value on or prior to the first dosing date of study drug, unless specified differently. If multiple measurements occur on the same day, the last nonmissing value prior to the time of first dosing of study drug will be considered as the baseline value. If these multiple measurements occur at the same time or the time is not available, the average of these measurements (for continuous data) will be considered the baseline value. For the efficacy endpoints, if no measurements occur prior to the time of first dosing of study drug, the first nonmissing value on the first dose date of study drug will be considered as the baseline value.
- For postbaseline values:
  - The record closest to the nominal day for that visit will be selected.
  - If there are 2 records that are equidistant from the nominal day, the later record will be selected.
  - If there is more than 1 record on the selected day, the average will be taken, unless otherwise specified.

If multiple valid, non-missing, categorical measurements exist for one visit, records will be chosen based on the following rules if a single value is needed:

- For baseline, the last available record on or prior to the date of the first dose of study drug will be selected. If there are multiple records at the same time or no time recorded on the same day, the value with the lowest severity will be selected unless otherwise specified.
- For postbaseline values:
  - The record closest to the nominal day for that visit will be selected.
  - If there are 2 records that are equidistant from the nominal day, the later record will be selected.
  - If there is more than 1 record on the selected day, the value with the worst severity will be used.

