6.7.6. Safety Labs

When available, the most recent laboratory values (obtained ≤ 7 days prior to Screening) may be used for eligibility assessment, with the exception of RSV results and pregnancy testing. If an existing laboratory value is not available for eligibility assessment, the test will be performed using the local hospital laboratory. All testing of samples obtained after the Screening assessments (with the exception of an additional local troponin test on Day 1/Baseline and Day 28/End of Study) will be performed at a central laboratory selected by GSI.

Central laboratory testing of blood specimens for safety analysis will include CBC, sodium, potassium, chloride, CO₂, BUN, creatinine, glucose, AST and ALT, alkaline phosphatase, total bilirubin and CK on Days 1/Baseline, 7, and 14 (pre-dose) and on Days 21 and 28/End of Study.

Local laboratory testing of troponin will also be done at Day 1/Baseline and Day 28/End of Study for timely safety evaluation by the investigator. Local troponin testing will be done in accordance with the standard assay available at the site.

If the subject is seen at the site for any reason (eg, hospitalization, clinic, or site visit) between Days 2 to 14, a blood draw for troponin measurement is required. If the subject is at the site on more than 1 occasion between this timeframe, only 1 protocol-mandated measurement is required, but it should be obtained at the earliest feasible time and during the same study visit as the ECG measurement described below.

Samples will be sent to the local lab at the clinical site for troponin analysis using the laboratory-based assay specific to the local trial site (eg, troponin I or T). Point-of-care “rapid” troponin tests are not acceptable for protocol-mandated troponin testing. The baseline troponin test must be pre-dose. Troponin testing done for the purposes of patient care on the same day as a protocol-required test day may be used, provided the test is completed at the protocol-directed time and is a laboratory-based assay. Troponin results should be verified before the subject leaves the clinical site in case a troponin value is positive and further medical care is advised. Any additional troponin measures obtained for the purposes of patient care also require collection.

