6.7.7. Electrocardiogram (ECG)

As part of safety testing, at Day 1/Baseline a pre-dose 12-lead ECG will be performed on the clinic or local hospital equipment. A second 12-lead ECG will also be performed at Day 28/End of Study.

If the subject is seen at the site for any reason (eg, hospitalization, clinic, or site visit) between Days 2 to 14, a 12-lead ECG is required. If the subject is at the site on more than 1 occasion between this timeframe, only one protocol-mandated ECG measurement is required, but it should be obtained at the earliest feasible time and during the same study visit as the troponin measurement described above. ECG testing done for the purposes of patient care on the same day as a protocol-required test day may be used, provided the test is completed at the protocol-directed time. ECG results should be verified before the subject leaves the clinical site in case further medical care is advised. Any additional ECG measures obtained for the purposes of patient care also require collection.

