### **7.5. Electrocardiogram Assessment**

Number and percent of subjects with new ECG abnormalities at postbaseline visits including those assessments obtained for the purpose of standard of care will be summarized by treatments. Only subjects with baseline ECG assessments will be included in this analysis.

A shift table of the central ECG assessments at postbaseline visit including those assessments obtained for the purpose of standard of care compared with baseline values will be presented by treatment group using the following categories: normal, abnormal, no new abnormality, new abnormality, or missing. The number and percentage of subjects in each cross-classification group of the shift table will be presented. Subjects with a missing value at baseline or postbaseline will not be included in the denominator for percentage calculation. No formal statistical testing is planned.

A by-subject listing for ECG central assessments and ECG abnormalities, including those not required by the protocol (ie, standard of care), will be provided by subject ID number and visit in chronological order.

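### The SAP's categorical baseline rule is tied to the first-dose date, not the dosing time, so a post-dose Day 1 ECG or troponin category can become the baseline

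*SAP*

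**What the plan says.** SAP 3.8.3 has two baseline rules. For continuous data recorded on the dosing day, the baseline is chosen by dosing time: "If multiple measurements occur on the same day, the last nonmissing value prior to the time of first dosing of study drug will be considered". For categorical data: "For baseline, the last available record on or prior to the date of the first dose of study drug will be selected". The categorical rule goes on to a tie-break, under which the least severe record is taken: "If there are multiple records at the same time or no time recorded on the same day, the value with the lowest severity will be". The categorical rules come into play under this condition: "If multiple valid, non-missing, categorical measurements exist for one visit, records will be chosen based on the following rules if a single value is needed".

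SAP 7.5 and 7.6 analyse ECG and troponin as categories in shift tables against baseline, and neither section defines a baseline of its own. SAP 7.5 also counts "new ECG abnormalities at postbaseline visits including those assessments obtained for the purpose of standard of care"; SAP 7.6 likewise brings standard-of-care troponins into the postbaseline side.

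The protocol fixes the timing of the reference measurement. Section 6.7.7: "at Day 1/Baseline a pre-dose 12-lead ECG will be performed on the clinic or local hospital equipment". Section 6.7.6: "The baseline troponin test must be pre-dose". Section 8.7.3 compares ECG measurements with screening or pre-dose Day 1 values.

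**The concern.** The categorical rule lets a record taken after the first dose serve as baseline, even when the required pre-dose record exists. An on-drug finding would then be treated as the subject's starting state. Day 1 carries the largest single dose of the regimen (200 mg, against 100 mg on later days), so the first hours after it are a period that a cardiac safety table should classify correctly.

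The tables at stake are the ECG shift table (15.11.9.1), the table of new ECG abnormalities (15.11.9.2) and the troponin shift table (15.11.6.6). Cardiac events are a prespecified safety interest (SAP 7.1.7 and Appendix 3). The planned DMC safety review was cancelled (SAP 2.1 and 7.7), so the end-of-study tables are the main summary of this question.

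**Working it through.** The plan gives no figure to reproduce here. The check compares the rules and then enumerates what each would do.

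**Step 1. Baseline rules side by side.**

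| Data type | Source | Anchor |
|---|---|---|
| Continuous, same day | SAP 3.8.3 | time of first dosing |
| Numeric laboratory values | SAP 7.2.1 | date/time of first dose |
| Vital signs | SAP 7.3 | date/time of first dose |
| Categorical (ECG, troponin shift) | SAP 3.8.3 | date of first dose only |

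The categorical rule is the outlier.

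**Step 2. Can a post-dose record sit under the Day 1 visit?** The protocol schedules no post-dose ECG or troponin on Day 1. It does require any extra ECG or troponin done for patient care to be collected (6.7.6, 6.7.7). It lists collection of standard-of-care cardiac tests among the Day 1 procedures after dosing (6.1.2.2), beside a PK sample at 2 to 4 hours post-dose. Appendix 2 marks that collection in the Day 1/Baseline column. So such a record can exist and can be filed under Day 1.

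**Step 3. Enumerate the outcomes.** Assume both Day 1 records are timed and filed under Day 1, and that a new abnormality means baseline normal (N) with any postbaseline record abnormal (A).

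- Date rule (as written): baseline = post-dose Day 1; postbaseline = Day 28.
- Time rule: baseline = pre-dose Day 1; postbaseline = post-dose Day 1 and Day 28.

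| Pre-dose | Post-dose | Day 28 | New, date rule | New, time rule | Differs |
|---|---|---|---|---|---|
| N | N | N | no | no | |
| N | N | A | yes | yes | |
| N | A | N | no | yes | missed |
| N | A | A | no | yes | missed |
| A | N | N | no | no | |
| A | N | A | yes | no | false |
| A | A | N | no | no | |
| A | A | A | no | no | |

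Three of the eight patterns change: two new abnormalities are missed and one false one is created. These are logical patterns, not probabilities. A subject with only the scheduled pre-dose record gets the same baseline under both rules.

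**Step 4. Weight of one subject.** Sixty subjects randomised 2:1 give 60 × 2/3 = 40 on presatovir and 60 × 1/3 = 20 on placebo. One misclassified subject is 1/40 = 2.5 percentage points or 1/20 = 5 percentage points. The actual table denominators may be smaller, because subjects with a missing baseline or postbaseline value are excluded from the shift-table percentages.

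**The case against.** The strongest reply is that SAP 3.8.2 already prevents this: "Any data relating to unscheduled visits will not be assigned to a particular visit or time point". Its exception for baseline admits only unscheduled visits before the first dosing. A post-dose test on Day 1 is not on the schedule, so it could be said never to reach the Day 1 visit. This narrows the reach but does not close the gap. Protocol 6.6 describes unscheduled visits as returns to the clinic or hospital between scheduled visits, and a test later in the Day 1 visit is not that. Once filed under Day 1, the record falls under the categorical rule.

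A second reply is that SAP 7.5 and 7.6 mention standard-of-care results only on the postbaseline side, and that troponin is a laboratory test covered by SAP 7.2.1. The first part shows the likely intent, but neither section says which record is the baseline. The second part is arguable, but the heading of 7.2.1 limits it to numeric results and the troponin table is categorical.

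A third reply concerns the consequences, and most of it stands. The tables are descriptive, with no formal testing. SAP 7.5 and 7.6 list every ECG and troponin by subject, including standard-of-care ones. An abnormal result with symptoms that meets the adverse event definition must be reported as one (Protocol 7.1.3 and 7.5); with onset on or after the drug start date it is treatment-emergent (SAP 7.1.5.1) and eligible for the cardiac event summary (SAP 7.1.7).

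A reader might infer that every Day 1 post-dose abnormality is hidden and that the tables lean towards no effect of presatovir. The documents do not support either. Masking needs a timed post-dose record filed under Day 1 and a normal pre-dose record. Where times are missing, the lowest-severity tie-break keeps the normal record as baseline. The rule takes no account of arm and can also create a false new abnormality. For ECG, the SAP names new abnormality as a category of the central assessment without saying how it is set, so a central reading made against the pre-dose tracing might still flag the change.

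**Conclusion.** The rule is wrong as written, and the severity is low. On its literal wording it can choose a post-dose ECG or troponin category as baseline, which conflicts with the protocol's pre-dose reference and with the other baseline rules in the SAP. The effect is conditional: it needs a non-scheduled test after dosing on Day 1, recorded with a time and filed under that visit. The classification then changes in three of eight patterns, in both directions and in either arm.

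The documents give no rate for such tests, so the number of affected subjects cannot be estimated; it is probably small. Each one would move a percentage by about 2.5 points on presatovir or 5 points on placebo. The pattern count assumes that a new abnormality is derived by comparison with the selected baseline, which is plain for troponin but not stated for ECG. The error would sit in the summary tables; the listings would still show the record, and the adverse event tables would show any event that met the reporting definition.

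**What to change.** In SAP 3.8.3, define the categorical baseline as the last available record before the date and time of the first dose of study drug, and keep the existing tie-break for records with missing times. In SAP 7.5 and 7.6, state that Day 1 ECG and troponin records timed after the first dose count as postbaseline.

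The cost is a sentence or two in the SAP and a date/time comparison in the programs. No new assessments are needed, because the protocol already requires the pre-dose ECG and troponin.

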## **4. SUBJECT DISPOSITION**

### **4.1. Subject Enrollment and Disposition**

A summary of subject enrollment will be provided by treatment group for each country, investigator within a country, and overall. The summary will present the number and percentage of subjects enrolled. For each column, the denominator for the percentage calculation will be the total number of subjects analyzed for that column.

A similar enrollment table will be provided by randomization stratum. The denominator for the percentage of subjects in the stratum will be the total number of randomized subjects. If there are discrepancies in the value used for stratification assignment between the IWRS and the clinical database, the value collected in the clinical database will be used for the summary. A listing of subjects with discrepancies in the value used for stratification assignment between the IWRS and the clinical database at the time of data finalization will be provided.

The randomization schedule used for the study will be provided as an appendix to the CSR.

A summary of subject disposition will be provided by treatment group. This summary will present the number of subjects screened, the number of subjects who met all eligibility criteria but were not randomized with reasons subjects not randomized, the number of subjects randomized, and the number of subjects in each of the categories listed below:

- Full Analysis Set
- Safety Analysis Set
- Per-Protocol Analysis Set
- PK Analysis Set
- Completed study drug
- Did not complete study drug with reasons for premature discontinuation of study drug
- Completed Main Study Portion
- Did not complete the Main Study Portion with reasons for premature discontinuation of Main Study Portion
- Completed Extended Viral Load Monitoring Period
- Did not complete the Extended Viral Load Monitoring Period with reasons for premature discontinuation of Extended Viral Load Monitoring Period

For the status of study drug and main study portion completion and reasons for premature discontinuation, the number and percentage of subjects in each category will be provided. The denominator for the percentage calculation will be the total number of subjects in the Safety Analysis Set corresponding to that column.

The following by-subject listings will be provided by subject ID number in ascending order to support the above summary tables:

- Reasons for premature study drug or study discontinuation
- Reasons for screen failure (will be provided by screening ID number in ascending order)

#### **4.2. Extent of Study Drug Exposure and Adherence**

Extent of exposure to study drug will be examined by assessing the total duration of exposure to study drug and the level of adherence to the study drug specified in the protocol. The data collected in eCRF will be used for the analyses.

##### **4.2.1. Duration of Exposure to Study Drug**

Total duration of exposure to study drug will be defined as last dose date minus first dose date plus 1, regardless of temporary interruptions in study drug administration, and will be expressed in days using up to 1 decimal place (eg, 4.5 days). If the last study drug dosing end date is missing, the latest date among the study drug end date, clinical visit date, laboratory sample collection date, and vital signs assessment date that occurred during the on-treatment period will be used.

The total duration of exposure to study drug will be summarized using descriptive statistics (number of subjects [n], mean, SD, median, Q1, Q3, minimum, and maximum), and using the number and percentage of subjects exposed through the following time periods: Day 1(Baseline), Day 3, Day 5, Day 7, Day 9 and Day 14. Summaries will be provided by treatment group for the Safety Analysis Set.

No formal statistical testing is planned.

